### ***Urine testing***

A urine samples will be obtained at each visit for future testing to help refine models of prediction of PrEP adherence in cisgender women based on urine. The participant will be asked to void a small amount of urine into a sterile specimen container per standard procedures.

### ***Hair collection***

A small amount of hair (about 50-100 strands) will be collected from the occipital portion of the scalp in order to refine models for prediction of long-term PrEP adherence in cisgender women based on hair. The hair will be cut from as close to the scalp as possible with scissors. The hair that is cut will be taken from underneath the top layer of hair to minimize visibility of the removed hair. Measuring TFV/FTC exposure in small hair samples is feasible and acceptable in Kenya PrEP trials.

### ***Blood for DNA***

Blood for DNA will be obtained during Week 1 visit from participants who consent to sample storage for future testing. Genomic DNA will be isolated using a commercially available kit, according to standard manufacturer protocol. The DNA will be analyzed pharmacogenetic studies of protein drug transporters, and will not be used for whole genome sequencing. Only gene DNA analysis related to antiretroviral drug disposition or treatment response (drug transporters) will be evaluated. An addendum consent will be used to obtain informed consent for future testing.

### **5.3 Procedures for participants identified as HIV infected and/or pregnant**

While it is expected to be very rare, this study may identify persons who become infected with HIV-1 during follow-up. Study staff will provide participants with their HIV test results in the context of post-test counseling. In the case of a positive test, a blood sample will be obtained for HIV drug resistance testing conducted through the standard national GEMS protocol for drug resistance surveillance. These results will be communicated to participants as soon as they are available. Persons identified as HIV infected during the study will be initiated on free HIV treatment and will also be referred to nearby HIV care services for follow up at completion of this trial. For participants who are pregnant and become infected with HIV during study follow-up, every effort will be made to facilitate immediate access to programs for preventing mother-to-child HIV transmission for appropriate antiretroviral treatment to reduce the probability of HIV transmission from mother to child.

## **6 SAFETY MONITORING AND ADVERSE EVENT REPORTING**

### **6.1 Safety Monitoring**

A Protocol Safety Review Team (PSRT) discuss and regularly monitor safety issues that arise during the study, as outlined in this section. The PSRT will consist of the Principal Investigators, a study coordinator, a Gilead representative, and a Study Safety medical Officer. Email communications or calls will be held approximately every month, or as needed to discuss safety or study-related concerns, as described below. Conference calls will be held approximately every 6 months to summarize cumulative safety reports and enrollment. These reports will include all clinical and laboratory adverse events; social harms; enrollment including gender/ethnicity; and disqualified/excluded individuals. The Seattle-based Study safety monitor will review all safety data, and will prepare routine study conduct and safety reports for the PSRT, which will meet by conference call approximately every 6 months or as needed. The study site Investigators are responsible for continuous close monitoring and management of AEs in conjunction with IoRs. Sites are required to have detailed SOPs describing methods for AE reporting and toxicity management to ensure that AEs are reported and managed in accordance with the protocol and for alerting the PSRT if unexpected concerns arise

## **6.2 Clinical Data Review**

A multi-tiered safety review process will be followed for the duration of this study. The study site investigators are responsible for the initial evaluation and reporting of safety information at the participant level, and for alerting the PSRT if unexpected concerns arise.

Participant safety data will also be monitored by the Seattle-based Study safety monitor, who will review incoming safety data for completeness and consistency on an ongoing basis. Events identified as questionable, inconsistent, or unexplained will be queried for verification.

The Seattle-based Study safety monitor will prepare routine study conduct and safety reports for the PSRT, which will meet by conference call approximately every 6 months and will review accrual and retention data, as well as safety data. More frequent or ad hoc reviews of safety data may be conducted by the PSRT as needed. A recommendation to stop the trial may be made by the PSRT at any such time that the team agrees an unacceptable type and/or frequency of AEs has been observed. If at any time a decision is made to discontinue the study product in all participants, the protocol chair will notify appropriate regulatory agencies, as well as the site IoRs, who will notify the responsible IRBs expeditiously.

## **6.3 Adverse Event Definition and Reporting**

An adverse event (AE) is defined as any untoward medical occurrence in a clinical research participant administered an investigational product and which does not necessarily have a causal relationship with the study product (TAF/FTC). As such, an AE can be an unfavorable or unintended sign (including an abnormal laboratory finding, for example), symptom or disease temporally associated with the use of an investigational product, whether or not considered related to the product.

Study participants will be provided a 24-hour telephone number and contact information and instructed to contact the study clinician to report any AEs they may experience. For life-threatening events, they will also be instructed to seek immediate emergency care. Where feasible and medically appropriate, participants will be encouraged to seek evaluation where the study clinician is based, and to request that the clinician be contacted upon their arrival. With appropriate permission of the participant, whenever possible, records from all non-study medical providers related to AEs will be obtained and required data elements will be recorded on study CRFs. All participants reporting an AE will be followed clinically, until the AE resolves (i.e., returns to baseline) or stabilizes.

Study site staff will document AEs in source documents and the appropriate e-CRF. Grade 1 and higher clinical AEs, Grade 2 and higher laboratory AEs, and any AE (clinical or laboratory) that leads to a study product hold (temporary or permanent) that are reported by or observed in enrolled (defined as after randomization has occurred) study participants will be captured on AE e-CRFs regardless of their severity and presumed relationship to the study product. AE severity will be graded per the DAIDS Table for Grading Adult and Pediatric Adverse Events, Version 2.1 corrected, July 2017.

## **6.4 Relationship to Study Product**

Relatedness is an assessment made by a study clinician of whether or not an adverse event is related to the study product. The relationship of all AEs to the study product will be assessed per the clinical judgment of the investigator based on the package insert and investigator's brochure.

## **6.5 Grading Severity of Events**

The Division of AIDS Table for Grading the Severity of Adult and Pediatric Adverse Events, Corrected Version 2.1, July 2017, will be used for determining and reporting the severity of adverse events. The DAIDS grading table is available on the DAIDS RSC website at <https://rsc.niaid.nih.gov/clinical-research-sites/daids-adverse-event-grading-tables>.

## **6.6 Serious Adverse Event (SAE)**

All SAEs as defined by ICH guidelines will be reported regardless of relationship to the study agent(s), and are as follows:

- Results in death,
- Is life-threatening,
- Requires inpatient hospitalization or prolongation of existing hospitalization,
- Results in persistent or significant disability/incapacity, or
- Is a congenital anomaly/birth defect
- Important medical events that may not be immediately life-threatening or result in death or hospitalization but may jeopardize the patient or may require intervention to prevent one of the outcomes listed in the definition above. Such determination may be made through medical or scientific judgment. Examples include the following: intensive treatment in an emergency room or at home for allergic bronchospasm; blood dyscrasias or convulsions that do not result in hospitalization; development of drug dependency or drug abuse; etc.

## **6.7 Discontinuation of Study Medication**

Subjects may withdraw from the study at any time. Any participant who prematurely discontinues study medication (for toxicity or pregnancy) should be followed for study duration. Subjects who become pregnant or who acquire HIV infection will have study drug discontinued but will be followed to determine the pregnancy outcome.

## **6.8 Discontinuation of study drug with toxicity**

Grade I or II toxicity will be managed in consultation with a clinician on the protocol. The clinician may add follow up testing and evaluations, as medically indicated. Study drug can be continued except as noted below.

Grade III toxicities will be communicated to the PSRT and managed under the direction of a study physician. Follow up testing and evaluations will be added, as medically indicated. The toxicity will be evaluated for subject safety. If the adverse event may put the subject at increased risk, or jeopardizes the study's intent, even if not related with study drug, the subject will discontinue study drug. The PSRT will decide whether study drug can be restarted. If the adverse event is deemed not to be a significant health risk, the PSRT may recommend continuing study drug with close monitoring.

Grade IV toxicities will be communicated to the PSRT and managed under the direction of a study physician. If a grade IV event is related to the study drug, the participant will permanently discontinue the study drug and will be followed as medically indicated. If the grade IV is not related to the study drug, the PSRT will recommend whether study drug can be continued with close monitoring, or permanently/temporarily discontinued.

Participants who discontinue drug permanently due to a study drug-related AE will be followed until AE resolves or stabilizes and then the subject will be discontinued from the study.

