### **6.8.3 Grade 4**

For all Grade 4 laboratory-identified or clinical toxicities, TAF-FTC will be withheld unless it is determined to be not related. If a Grade 4 laboratory toxicity is not confirmed by repeat testing, it should be managed per algorithm for the new toxicity grade. Participants with Grade 4 AEs will be followed until the event resolves to baseline or stabilizes. Study drug may be restarted in the event of the resolution of a Grade 4 AE back to Grade 1, after consultation with the site investigator and other members of the PSRT. If the toxicity recurs to Grade 3 or higher after TAF-FTC is restarted and is considered to be related to TAF-FTC, the study medication will be permanently discontinued.

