## **6.9 Reporting Requirements for this Study**

For each study participant, the SAE/EAE reporting period begins at Enrollment (Day 0) and ends when the participant's follow-up in the study ends. All reportable SAEs occurring during the study reporting period will be reported to the principal investigator

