## **8.13 Study Discontinuation**

The study also may be discontinued at any time by government or regulatory authorities, or site IRBs/ECs.

Subjects may withdraw from the study at any time. Depending on the time point and circumstances of a subject's withdrawal they will be asked to complete/offer an "Early Discontinuation/Exit Visit" to confirm safety and health status as the time of withdrawal. The study investigators can remove a subject at any time if they deem that the study is no longer in the subject's best interest or the subject is not adhering to the protocol. Discontinuation of a subject by the PI/Co-I(s) could be a result of but is not limited to the following:

- Subjects who become incarcerated while on the study.
- Subjects who acquire other infectious diseases (i.e. not HIV) while in the study will be reviewed by the PI/PSRT to confirm subject is still considered low-risk for HIV infection (See Exclusion criterion) This determination will be done by the PI/study physician.
- Subjects who are deemed to be non-compliant with the study medication(s) and/or procedures (e.g. 2 consecutive missed study visits or medication doses) may be discontinued from the study by the PI.
- Permanent study drug discontinuations for toxicity were described above. These participants will be followed until the completion of scheduled protocol study duration.
- Subjects who require an exclusionary medication during the study will be discussed among the PSRT. Participant's continued study involvement will be determined the PSRT and PI's.

The PSRT will be consulted if and when these circumstances arise.

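### Section 6.8 takes women out of the study once a drug-related AE settles, while 8.13 and 6.7 keep the same women to the scheduled end; secondarily, the 6.8.3 restart clause does not exclude related Grade 4 events

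*Combined protocol and SAP*

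**What the plan says.** **Follow-up after a permanent stop for toxicity.** Three places in the combined protocol and SAP address this.

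- Section 6.8, last paragraph, for permanent stops due to a drug-related AE: the woman "will be followed until AE resolves or stabilizes and then the subject will be discontinued from the study".
- Section 8.13: "Permanent study drug discontinuations for toxicity were described above. These participants will be followed until the completion of scheduled protocol study duration".
- Section 6.7: "Any participant who prematurely discontinues study medication (for toxicity or pregnancy) should be followed for study duration".

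Section 6.9 ties SAE/EAE reporting to follow-up: the period starts at enrollment "and ends when the participant's follow-up in the study ends". Section 5.2 schedules AE questionnaires through week 10.

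**Grade 4 events.** Section 6.8: "If a grade IV event is related to the study drug, the participant will permanently discontinue the study drug". For an unrelated Grade 4 event, 6.8 says "the PSRT will recommend whether study drug can be continued with close monitoring, or permanently/temporarily discontinued". Section 6.8.3: "For all Grade 4 laboratory-identified or clinical toxicities, TAF-FTC will be withheld unless it is determined to be not related". It continues: "Study drug may be restarted in the event of the resolution of a Grade 4 AE back to Grade 1". Before any restart, the PSRT and the investigator at the site must be consulted. Under 6.8.3 the stop becomes permanent only if a related toxicity returns at Grade 3 or higher after restart.

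**The concern.** Describing safety is primary objective 1. Under 6.8, the observation time of a woman with a drug-related toxicity is cut because she had that toxicity, so the loss depends on the outcome being described. Under 8.13 and 6.7 she stays. The site must choose, and two similar women could be handled differently.

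At stake are later or additional events after exit, including SAEs outside the shortened reporting window, and the post-drug PK samples at visits 13 and 14. On restart, a site relying on 6.8.3 alone could propose rechallenge after a related Grade 4 event, which 6.8 rules out. The PSRT would then be consulted on conflicting text.

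**Working it through.** The plan gives no figure to reproduce. The check compares the sections and counts scheduled assessments.

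**1. Do the follow-up rules cover the same women?** Section 6.8 covers permanent stops for a drug-related AE. Section 8.13 covers permanent stops for toxicity and points back to where they were described. Section 6.7 covers any early stop for toxicity or pregnancy. The 6.8 group lies inside both of the others. Sections 6.8 and 8.13 both use 'will'; 6.7 uses 'should'. Suppose her AE resolves at week 3: she must leave under 6.8 and must stay under 8.13. Treating 6.8 as a specific exception to a general 8.13 does not work, because 8.13 addresses those stops and prescribes the opposite. Section 3.8 also follows women who become pregnant to the scheduled end, so 6.8 is the outlier.

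**2. Scheduled assessments after exit.** Inputs are the visit lists in Section 5.2.2. AE assessment is at visits 2 to 12, which is 11 post-entry assessments. HIV tests are listed at visits 6, 10 and 12. The assumption is exit immediately after the named visit.

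| Exit after | AE assessments left | HIV tests left |
|---|---|---|
| Week 2 (visit 4) | visits 5–12: 8 of 11 | 3 |
| Week 4 (visit 6) | visits 7–12: 6 of 11 | 2 |
| Week 8 (visit 10) | visits 11–12: 2 of 11 | 1 |

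These are upper limits. An exit evaluation (Sections 3.7 and 8.13) could stand in for one HIV test. At most one creatinine test is lost, and none if it is done at exit.

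**3. SAE-reporting weeks after exit.** Section 5.2.2 describes visit 14 both as week 12–18 and as 2–8 weeks after the last dose.

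- Calendar clock, (12 to 18) minus exit week: 10–16, 8–14 and 4–10 weeks for exit at week 2, 4 and 8.
- Last-dose clock, with last dose at exit week L and scheduled visits kept to week 10: the end runs from max(10, L+2) to max(10, L+8). L=2: 10 − 2 = 8. L=4: 10 to 12, minus 4, is 6–8. L=8: 10 to 16, minus 8, is 2–8.

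Two discounts apply. On the calendar clock, 12 − 10 = 2 to 18 − 10 = 8 of the weeks fall after week 10, when scheduled AE assessment has ended for everyone. Over that stretch only passive reporting is lost. Also, the last dose normally precedes exit under 6.8. With last dose at week 6 and exit at week 8, the end is week 10 to 14 and the loss is 2–6 weeks, not 2–8. Up to week 10, the loss is 8, 6 or 2 weeks.

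**4. Grade 4 restart.** Section 6.8.3 withholds drug unless the event is determined to be not related, so the held events include related ones. The restart sentence refers to a Grade 4 AE without qualification. Section 6.8.2 uses the same hold, reintroduce and stop-on-recurrence sequence expressly for related Grade 3 events, so a reader may take 6.8.3 the same way. Section 6.8 makes a related Grade 4 event a permanent stop. The limit that would reconcile them is not written.

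**The case against.** The strongest case is that little is lost. The index AE is followed to resolution or stabilization under either rule (6.3), data to exit are used and permanent stops are replaced (3.8), and exit evaluations are provided for (3.7, 8.13). Section 8.5 calls for HIV testing as needed and at the final visits of dosing. All of this stands and limits the size of the point. None of it covers the time after exit, or says which rule governs.

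On restart, 6.8 is mandatory and 6.8.3 is permissive, so a team that never restarts breaches neither. The clause has a proper use for unrelated or not-yet-attributed events, since 6.8 lets the PSRT stop drug temporarily for an unrelated Grade 4 event. Section 6.8.3 also asks about relatedness at recurrence, which fits that reading, and the PSRT is told of every Grade 4 event. This largely stands.

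Stronger readings that a reader might infer are not supported:

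- *The safety result is invalidated.* A woman who exits this way already counts as having an AE, so a per-woman any-AE proportion is unchanged. Only later or additional events or event types can be missed.
- *Up to 16 weeks of active surveillance are lost.* That figure uses the latest calendar end and includes weeks with no scheduled AE assessment for anyone.
- *Only women with drug-related toxicity leave early.* Withdrawal, non-compliance, incarceration and investigator judgement are also routes out. What is distinctive is that 6.8 makes exit automatic because of a drug-related AE.
- *6.8.3 plainly authorises rechallenge after a related Grade 4 event.* The text leaves out a limit; it does not give that instruction.

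**Conclusion.** The follow-up contradiction is real, and nothing in the documents resolves it. If 6.8 is followed, an affected woman misses up to 8, 6 or 2 of 11 post-entry AE assessments for exit after week 2, 4 or 8. She also loses the rest of the passive SAE window and possibly post-drug PK visits. These counts assume exit immediately after the named visit.

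Few women are likely to be affected: the plan gives no event rate, and Section 8.5 describes serious side effects as a remote risk. The sample size and the dose-proportionality calculation do not change. The restart gap is secondary, because the clauses can be partly harmonised but the limiting condition is missing. The text should be corrected because it governs safety handling and the correction is cheap. It does not threaten the trial's main conclusions.

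**What to change.** 1. Replace the last paragraph of 6.8 with the 6.7/8.13 rule: every woman who permanently stops drug for toxicity, related or not, is followed to the end of scheduled follow-up and at least until the AE resolves or stabilizes.
2. Limit the 6.8.3 restart clause to Grade 4 events judged not related to study drug, including those held while relatedness was being determined.

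The cost is one wording amendment and no added participants. Compared with exit under 6.8, an affected woman attends at most the remaining scheduled visits: visits 5–14 (10), 7–14 (8) or 11–14 (4) for exit after week 2, 4 or 8.

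Two optional clarifications are not part of the correction. One is whether vaginal biopsies continue after drug stop; full follow-up would otherwise include 2 more after a stop by week 2, or 1 more after a stop between the week 4 and week 8 visits. The other is which visit 14 clock applies to women who stop early.

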### **6.8.1 AE Grades 1 or 2**

Grade I or II toxicity will be managed in consultation with a clinician on the protocol. The clinician may add follow up testing and evaluations, as medically indicated. Study drug can be continued except as noted below.

### **6.8.2 AE Grade 3**

TAF-FTC may be continued as directed by the site investigator if a Grade 3 toxicity is considered to be unrelated to the study medication. Study medication will be temporarily withheld if Grade 3 toxicity is considered to be related to the study medication. After a Grade 3 toxicity returns to Grade 1, the participant can be reintroduced to medication after consultation with the site investigator and other members of the PSRT. If a Grade 3 toxicity recurs and is considered to be related to study medication, TAF-FTC will be permanently discontinued.

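### Sections 6.8 and 6.8.2 apply different tests to Grade 3 toxicity, and in two situations one requires stopping study drug where the other permits continuing

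*Combined protocol and SAP*

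**What the plan says.** **Section 6.8** has its own Grade 3 paragraph. On handling: "Grade III toxicities will be communicated to the PSRT and managed under the direction of a study physician". If the event may raise the participant's risk, or threatens what the study sets out to do, then "even if not related with study drug, the subject will discontinue study drug". On restart: "The PSRT will decide whether study drug can be restarted". On continuing: "If the adverse event is deemed not to be a significant health risk, the PSRT may recommend continuing study drug with close monitoring". Relatedness enters only to be set aside.

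**Section 6.8.2** covers the same grade and turns on relatedness. If the event is unrelated: "TAF-FTC may be continued as directed by the site investigator if a Grade 3 toxicity is considered to be unrelated to the study medication". If it is related: "Study medication will be temporarily withheld if Grade 3 toxicity is considered to be related to the study medication". On restart: "After a Grade 3 toxicity returns to Grade 1, the participant can be reintroduced to medication after consultation with the site investigator", and the sentence goes on to add the other PSRT members. A recurrent, related Grade 3 toxicity leads to permanent discontinuation. Risk to the participant is not mentioned.

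**Section 6.1** defines the PSRT: "The PSRT will consist of the Principal Investigators, a study coordinator, a Gilead representative, and a Study Safety medical Officer".

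**The concern.** A Grade 3 event is the point at which site staff must decide whether the next dose is given. Here they have two instructions, built on different criteria, with nothing to say which comes first. Two sites, or one site on two days, could treat the same event differently, and each could cite the protocol.

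The data are affected as well. Describing safety is the first primary objective (section 2.3), and section 8.4 names related Grade 3 and 4 events and discontinuations among the safety measures. The choice of section can therefore change whether a discontinuation is recorded. It can also change who is replaced. Under section 3.8 a woman is replaced if she permanently discontinues, misses two consecutive scheduled doses, or misses a pharmacokinetic sample, and a hold or discontinuation may bring about any of these.

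**Working it through.** The plan gives no figure on this point, so the check sets the two rules side by side. Section 6.8's test (risk or threat to study intent, against not a significant health risk) is crossed with section 6.8.2's test (related, against unrelated).

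| Situation | Section 6.8 | Section 6.8.2 | Result |
|---|---|---|---|
| Related; raises risk or threatens study intent | Drug is discontinued; PSRT decides restart | Drug is temporarily withheld | Both stop; restart terms differ |
| Related; not a significant health risk | PSRT may recommend continuing | Drug is temporarily withheld | One permits continuing, the other requires withholding |
| Unrelated; raises risk or threatens study intent | Drug is discontinued | Site investigator may continue | One requires stopping, the other permits continuing |
| Unrelated; not a significant health risk | PSRT may recommend continuing | Site investigator may continue | Both allow continuing, by different routes |

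The sections conflict in 2 of 4 situations.

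**Does the text settle precedence?** Three places were checked.
- The proviso in section 6.8 pointing to exceptions further down, repeated in 6.8.1, is attached to Grades 1 and 2 only. It does not subordinate 6.8's Grade 3 paragraph to 6.8.2.
- Section 4.7 lets a clinician stop drug when continued use seems harmful, and has the PSRT consulted on further holding or recommencing. It gives no authority to continue where another section requires stopping.
- Section 8.13 refers back to the toxicity rules for permanent discontinuation and adds no ordering.

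**Who may allow continuation?** In 6.8 a study physician directs management and the PSRT may recommend continuing. In 6.8.2 the site investigator directs continuation of an unrelated event. By section 6.1 the PSRT is a body of several members, so one investigator's direction is not a PSRT recommendation.

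**What governs restart?** Section 6.8.2 refers to return to Grade 1 and then consultation. Section 6.8 leaves restart to the PSRT and gives no grade threshold.

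**Are 6.8's own conditions complementary?** Not strictly. An event could threaten the study's intent without being a significant health risk, and 6.8 alone would then point both ways. The four-cell table simplifies this; the overlap adds ambiguity and removes none.

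**Link to replacement.** Under the schedules in section 2.5, a two-day hold in the daily arm already covers two consecutive scheduled doses. In the two-dose arm, dosed on Monday and Tuesday, a Wednesday-to-Sunday hold covers none. So a temporary hold can lead to replacement, but need not. Section 3.8 caps replacement at 20% of the target: 0.20 × 54 = 10.8, so at most 10 women, against a planned 18 per arm.

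**The case against.** The strongest reply is that the two sections can be read together. Section 6.8 is the parent and 6.8.2 its Grade 3 subsection. In both conflicting situations a mandatory instruction meets a permissive one, and stopping drug complies with both. A permission to continue an unrelated event can naturally be read as limited by the parent section's requirement to stop when risk is raised, and section 4.7 gives the clinician a route to stop in any case.

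Much of this stands. A reader might infer that the sections issue opposite orders. They do not: no situation has one section ordering a stop and the other ordering continuation. The unrelated, raised-risk situation is the easier of the two to reconcile.

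The reply does not dispose of the point. The cumulative reading is an inference that the text never states. It also leaves the related, low-risk situation unresolved, because continuing there is allowed by 6.8 and barred by 6.8.2. If stopping is always the safe way to comply, the permissions to continue have no effect exactly where the sections disagree.

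The contrast in decision makers should not be pressed too far either. A reader might infer that the PSRT alone decides under 6.8 and the site investigator alone under 6.8.2. In fact 6.8 has a study physician directing management, and 6.8.2 brings the PSRT into restart, with wording that treats the site investigator as one of its members. The clear difference is who may allow continuation.

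**Conclusion.** The inconsistency is real and should be corrected. In 2 of 4 combinations of relatedness and risk, a site that continues drug complies with one section and breaches the other; in the remaining two, the restart terms or the route to continuation differ. The count treats 6.8's two conditions as complements, and it describes the text, not how often the problem will arise. The documents give no expected number of Grade 3 events, and section 8.5 expects the most likely side effects to be mild and reversible.

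A reader might also infer that every woman whose drug is stopped is replaced, or that her data are lost. Section 3.8 does not support either. Replacement needs a permanent discontinuation, two consecutive missed scheduled doses or a missed pharmacokinetic sample, and data from women who discontinue stay in the analyses. No effect on a primary estimate has been shown. What is at stake is consistent handling of a safety event and, secondarily, who is replaced.

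**What to change.** Reconcile sections 6.8 and 6.8.2 so that site staff have one consistent Grade 3 instruction. The revised text should state:
- how the risk and relatedness criteria combine, or which section prevails;
- who may allow study drug to continue;
- what governs restart.

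A rule using both criteria could be coherent, so the request is for consistency and not for a single trigger. Which clinical rule is right is for the sponsor to decide; this review takes no position on it. The cost is a protocol wording change, with no effect on sample size, visits or assays.
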